Study Design & Methods

This is a 3-year, randomized, double-blind, calcium and vitamin D controlled trial with the antiresorptive agent zoledronic acid (Reclast).

The study consists of 5 main visits (Screening, Randomization, Month 12, Month 24, and Month 36), with pre and post infusion safety check visits. Pre-infusion safety check visits will be done up to 2 weeks prior to receiving the annual IV study drug or placebo. Post-infusion safety check visits will be done 1-3 days after infusion.

We have chosen yearly intravenous zoledronic acid because it has been shown to significantly reduce vertebral fractures by 70%, all clinical fractures by 35%, hip fractures by 41% in the pivotal trial that included older healthy women. Additionally, in a sub-analysis including women \geq 75 years old, yearly zoledronic acid decreased vertebral fractures by 66% over 3 years. Moreover, fracture reduction after 2 and 3 infusions were 47% and 39%, respectively. Because nursing home patients are difficult to treat and resources are limited, the intravenous injection has several advantages. It does not require fasting, administration at a specific time of day, or sitting up, which are all significant practical advantages over a weekly oral bisphosphonate. All patients without liver abnormalities will be offered acetaminophen prior to the infusion and for 2 days post-infusion to decrease acute phase reactions and maintain the blind.

Rationale for yearly dose versus single dose: Despite the improvement in density over 2 years after a single dose in our initial ZEST study, we will follow conventional yearly dosing that demonstrated fracture reduction in the pivotal trials. In the event we do not find a fracture reduction benefit, we wanted to be certain that it would not be due to under-dosing.

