At the request of the DSMB, we will be offering a Follow-up Extension phase to this study to continue data collection on the skeletal health of participants in the ZEST II study. Therapy and blood work will not be provided throughout the follow-up extension. There will be a maximum of three visits in the follow-up extension. The number of visits that a participant will have can be determined by when they have completed their Month 36 visit. Participants who have completed the Month 36 visit on or before July 31, 2019 will have three follow-up visits. Participants who have completed the Month 36 visit on or before July 31, 2020 will have two follow-up visits. Participants who have completed the Month 36 visit on or before July 31, 2021 will have one follow-up visit. Participants who do not complete the Month 36 visit before August 1, 2021 will not be eligible to participate in the follow-up extension.

SKELETAL ASSESSMENTS

Fragility Fractures: From baseline to the end of follow-up, nonvertebral and clinical vertebral fractures will be identified by the electronic medical record alert and by Theradoc (a real-time, stand-alone clinical alert and decision support application used at UPMC LTC facilities, with custom rules to be written for this study to provide detection and identification of participants presenting to any UPMC facility so that generated alerts will be sent to the study team via e-mail). In addition, participants/charts will be queried at approx. 6 month intervals for clinical fragility fractures defined as a fracture following a fall from a standing or sitting height. All reported fractures will be verified by obtaining the radiology report confirming the fractures. We exclude fingers, toes, face, and skull fractures. All femur fractures will be examined for atypical fractures using ASBMR criteria (128).

Vertebral Fractures: We will use the presence of thoracic or lumbar vertebral fractures as determined by Vertebral Fracture Assessment (VFA is DXA-derived) as the primary classification of vertebral fracture performed annually (53, 73, 129). The fractures will be scored according to the method of Genant (130, 131) and considered a grade 1 mild vertebral deformity, a grade 2 moderate vertebral deformity, or a grade 3 severe vertebral deformity. We will assess vertebral fractures at baseline, 12, 24, and 36 months, as well as at follow-up visits 1, 2, and 3. Conventional x-rays or a MRI that demonstrates a fracture will also be used.

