Indices of Bone Mineral Metabolism: Serum will be assayed for 25-hydroxyvitamin D2/D3 for the secondary aim. We will collect serum for bone turnover markers at baseline and M36 for responder analysis for the exploratory aim (60, 65-67, 132, 133). To assess bone resorption, we will measure serum CTX. We will assess bone formation with P1NP. Serum will be archived for future analyses.

Trabecular Bone Score (TBS): TBS, a new gray-level texture measurement is evaluated in the same region of interest as the spine BMD using the iNsight Software version 1.9 (54-58). TBS utilizes the 2-D DXA spine images and provides 3-D microarchitectural images and parameters (57, 59). The precision for TBS ranged from 1.1 to 1.9% (55). In previous studies, TBS was independent of BMD for fracture prediction and significantly improved risk protection (80, 81). TBS is only minimally affected by sclerosis/osteoarthritis (57). For the exploratory aim, we will examine TBS from DXA images.

Eligibility Criteria

Inclusion Criteria:

Our goal is to include older women with osteoporosis or low bone mass (with fracture risk) unless there is a known contraindication to therapy. We will enroll ambulatory women age ≥ 65 years including those using assistive devices to maximize generalizability, if they:

- 1) Reside in long-term care (LTC) including Managed Senior Communities which provide the following: (a) An environment engineered to prevent falls (handrails, ramps) and are ADA accessible; (b) Facilitate access to medical attention (pull cords, life-alerts, or other electronic means); (c) ADA accessible transportation services available; (d) Provide or coordinate meals; (e) Secure building (automatically locked door or buzzer system, security cameras).
- 2) Have a) osteoporosis by axial bone density (spine, hip or forearm BMD T-score ≤ -2.5 SD)(99,100); or b) a previous adult fragility fracture of the spine or hip; or, c) would be treated based on FRAX (101,102) NOF treatment thresholds of a 10 year risk of $\geq 20\%$ for a major osteoporotic fracture or $\geq 3\%$ for hip fracture using femoral neck BMD (103).

Follow-up Extension Inclusion Criteria:

- 1) Complete Month 36 Visit on or before July 31, 2021.

Exclusion Criteria:

We will exclude:

- 1) Men because osteoporosis is less common in men and our initial ZEST 1 study only included women.
- 2) Institutionalized women with subacute illnesses surviving or discharged in < 3 years.

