Findings from the proposed trial will be most useful if (a) we can also identify a target sub-population of the long-term care that is most likely to benefit from zoledronic acid and/or least likely to experience side effects; and (b) we can speculate whether fracture reduction or non-reduction in women, despite improvement in BMD, depends on bone microstructure as measured by TBS. Therefore, using several techniques, some with an exploratory data mining philosophy, we will identify such sub-populations to address Aim 3(a). First, we will include all baseline clinical and laboratory characteristics, one-at-a-time, as an additional fixed effect in the models above, along with an interaction term with treatment group. Statistical significance of the interaction term will be interpreted as a patient baseline characteristic whose levels exhibit potentially differential treatment effects and/or safety profiles. Second, we will stratify analyses by such baseline criteria to actually obtain preliminary estimates of subgroup-specific treatment effects/safety differences. Third (data mining), using only the active arm, we will fit a series of logistic regression models using the SAS® LOGISTIC procedure and classification tree models using Salford Predictive Miner® software (Salford Systems, Inc., San Diego, California) with incident fracture as the dichotomous response variable; and baseline characteristics as predictors. Logistic models are more efficient when associations are linear, and hard-to-discover higher order interactions and non-linearity and/or multicollinearities among predictors do not exist, while classification tree models are more efficient when they do exist. Thus we will use both methods to obtain areas under the receiver operator characteristic curve (AUROCC) to quantify predictive accuracy, and use the results from the method with a greater AUROCC. For logistic regression we will use the backward elimination and for classification trees minimum misclassification-complexity cost tree to guard against overfitting. We will use the method of DeLong to obtain statistical significance of the differences in predictive accuracy between the models. For predicting improvements in continuous BMD change outcomes, we will employ a similar approach but with standard multiple linear regression and regression tree models and proportion of explained variance (R²) to quantify predictive accuracy.

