For Aim 3(b), the association between zoledronic acid, BMD, TBS and fracture reduction will be explored in two ways. First, we proposed above to examine the effect of the study drug on TBS with standard linear models. Second, using only the active arm of the trial, we will fit a negative binomial model with number of fractures within 3 years as the dependent variable; and baseline BMD, 3-year change in BMD, baseline TBS, and 3-year change in TBS as independent variables. The statistical significance of regression coefficients for TBS measures will be interpreted as evidence supporting that fractures over a 3-year period depend on TBS and its changes over the same period independent of BMD.

Exploratory Analyses: We will perform exploratory analyses to assess the robustness of results and make more refined conclusions. For example, we will stratify adverse event and fracture

analyses to identify any differences between short- and long-term effects and/or within organ systems.

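### The exploratory Aim 3(b) model takes 3-year TBS change as something fractures depend on, but that change is complete only at month 36 and cannot show direction

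*Protocol*

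**What the plan says.** The Aim 3(b) paragraph of the protocol's Statistical Considerations describes a negative binomial model in the active arm. The outcome is "number of fractures within 3 years as the dependent variable", and the model has "baseline BMD, 3-year change in BMD, baseline TBS, and 3-year change in TBS as independent variables". Significant TBS coefficients are to be interpreted as "evidence supporting that fractures over a 3-year period depend on TBS and its changes over the same period independent of BMD". No restriction by fracture type is given, and the primary outcome counts vertebral and nonvertebral fractures together.

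The section on TBS says that it "is evaluated in the same region of interest as the spine BMD". On vertebral fractures, the Skeletal Assessments say "We will assess vertebral fractures at baseline, 12, 24, and 36 months", with thoracic and lumbar levels both included.

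The aim is introduced modestly: "we can speculate whether fracture reduction or non-reduction in women" depends on bone microstructure. The SAP repeats only the statistical overview and adds nothing on Aim 3(b).

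**The concern.** A predictor that is said to explain an outcome should be fixed before the outcome occurs. Here the change in TBS runs over the same three years as the fracture count and is known only at the end. The same holds for the change in BMD, which is the term meant to isolate TBS from BMD.

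There may also be a measurement route. If a counted vertebral fracture lies inside the region from which TBS is read, it could move the month-36 reading. Outcome and predictor would then be linked even if TBS change had no bearing on fracture.

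At stake is the answer to Aim 3(b)'s own question. If the rule is followed as written, a change that came after the fractures could be reported as something the fractures depended on.

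**Working it through.** **Timing, from the text alone**

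- Outcome window: baseline to month 36.
- Baseline TBS and baseline BMD: known before any counted fracture.
- 3-year changes in TBS and BMD: month-36 reading minus baseline, so complete only at or after the last counted fracture.
- Nothing in either document lags the change terms or limits the reading of their coefficients.

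This part needs no simulation. The change coefficients describe association only.

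**Region route, by simulation**

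The documents give no sample size, power or event count for Aim 3(b), so there is no planned figure to reproduce. Active arms were simulated with no true TBS effect, and each lumbar fracture shifted the month-36 TBS by a set amount. Each setting had 2,000 runs, with Wald tests at two-sided 0.05.

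Inputs from the protocol:
- Nonvertebral rate 11%/year (Scientific Background). Also 11% × (1 − 0.35) = 7.15%, applying the cited reduction in all clinical fractures.
- Cited vertebral reductions of 66% and 70% (Study Design & Methods).
- TBS precision 1.1 to 1.9%; 1.5% used.

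Assumed:
- 150 or 250 women assigned; loss 15%/year.
- Untreated vertebral rate 5%/year, giving a treated rate of 5% × 0.34 = 1.7% or 5% × 0.30 = 1.5%; run at 1.6%. Rates of 2.5% and 5% were also run; 5% means no vertebral efficacy.
- Half of vertebral fractures lumbar; frailty variance 0.7, shared by all fracture types.
- SD of true TBS change 2.5%; baseline TBS SD 8%.
- Shift per lumbar fracture 0, 2 or 4%.

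False significance of the TBS-change term, all fractures, TBS lowered (%, n=150 / n=250):

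| Vertebral; nonvertebral rate per year | No shift | 2% shift | 4% shift |
|---|---|---|---|
| 1.6%; 11% | 5.4 / 5.9 | 6.2 / 6.5 | 8.5 / 10.4 |
| 1.6%; 7.15% | 5.9 / 6.2 | 7.9 / 7.1 | 11.0 / 14.0 |
| 2.5%; 11% (n=250 only) | 5.9 | 9.0 | 16.9 |
| 5%; 11% | 6.4 / 5.7 | 12.9 / 15.3 | 27.8 / 41.6 |

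- With TBS raised instead (n=250), the 2% and 4% shifts gave 7.6% and 11.0% at 1.6%/year, and 16.0% and 40.6% at 5%/year.
- In the first row, a 2% shift adds 0.8 and 0.6 points. The simulation standard error of such a difference is about √(2 × 0.06 × 0.94 / 2000) = 0.0075, or 0.75 points, so neither is distinguishable from no effect.
- Few fractures carry the route. At 1.6%/year the lumbar rate is 0.8%, so the expected number in women with month-36 readings is 150 × 0.85³ × 3 × 0.008 = 2.2, or 3.7 for 250 women. At 5%/year it is 6.9 or 11.5.
- With nonvertebral fractures only, the change term was significant in 5.0–6.8% of runs with no shift, 4.9–6.6% at 2% and 5.2–8.2% at 4%. The remainder comes from the shared frailty.
- The baseline TBS term stayed at 4.1–6.6% in the plan's model.

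A second simulation used other assumptions: 100 or 200 women with month-36 data, mean TBS 1.20, 10% or 25% of fractures in the region, 300 runs per setting, and 0–25% of fits dropped for non-convergence. With no shift, false significance was 2–5%. With a shift of ±0.02 units (0.02/1.20 = 1.7%) it was 7–11% at a 10% share and 17–44% at 25%. With a shift of 0.05 it was 18–36% and 56–93%. The sign of the spurious association followed the assumed shift.

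A landmark version used 12-month TBS change against fractures in months 12–36, adjusted for earlier fractures. It gave 7.7%, 8.4% and 7.6% at shifts of 0, 0.02 and 0.05, so it did not depend on the shift. Those rates are about 2.0 to 2.6 simulation standard errors above 5% (√(0.05 × 0.95 / 274) = 1.3 points). The excess is present at zero shift, so the region route does not cause it.

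**The case against.** **The analysis is exploratory.** The protocol says it will explore and speculate, and depending on TBS could mean no more than regression dependence. This stands as a limit on severity. It does not remove the point, because the interpretation sentence still turns a significance test into a statement that fractures depend on TBS change.

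**The region route is not in the documents.** This stands in full. A reader might infer that counted lumbar fractures do distort TBS, so that a significant change term would be an artefact. The documents do not support that. They do not say that a fracture alters TBS, or by how much, or in which direction. They place TBS in the spine region without saying lumbar. The statement that "TBS is only minimally affected by sclerosis/osteoarthritis" concerns degenerative change and settles nothing about fracture in either direction.

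**The large inflation figures need unfavourable assumptions.** This also stands. In the 2,000-run simulation, 28–42% requires a 4% shift and no vertebral efficacy. At 1.6%/year with a 2% shift the increase is about 1 to 2 points, partly within simulation error.

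**The nonvertebral-only repeat does not restore time order.** Correct: those fractures also precede or coincide with the month-36 scan. The repeat checks the region route only. The landmark analysis is the version that puts change before fracture.

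**Conclusion.** The point holds on timing and is minor. A significant 3-year TBS-change coefficient cannot show that fractures depend on TBS change. Conditioning on BMD change over the same period does not secure independence from BMD; if that BMD is measured at the spine, it also shares the region problem. This conclusion needs no assumption beyond the protocol's own definitions.

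The region route is a possibility, with an effect from about nil to large according to the assumed shift, vertebral rate and lumbar share. No single inflation figure should be relied on.

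A reader might also infer that the whole model, baseline TBS included, is void. That goes too far. Baseline TBS precedes the fractures, and its false-significance rate stayed near nominal (4–7% in the 2,000-run simulation, 2–8% in the second). Its limitation is different: in the plan's model it is estimated jointly with the change terms, and only in women who reach a month-36 reading.

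The primary, secondary and safety analyses are unaffected.

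**What to change.** Replace the interpretation sentence with wording such as:

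> Any statement that fracture incidence depends on TBS, given BMD, will rest on a negative binomial model with baseline TBS and baseline BMD, in all women assigned to zoledronic acid who have a baseline scan, with log follow-up time to month 36 as offset. The model containing 3-year TBS and BMD changes will be reported as a non-directional association, with the number of women who have month-36 readings, and repeated counting nonvertebral fractures only. The repeat does not establish time order. If TBS is available from an earlier scan, any statement about TBS change will rest on a landmark analysis relating change up to that scan to fractures after it.

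The offset follows the Main Analyses. Including women with partial follow-up follows the Primary Outcome section; once the change terms are out of the model, a month-36 reading is no longer needed. The documents do not say whether TBS is read from scans before month 36, so the landmark analysis is conditional.

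If the change term is significant only when vertebral fractures are counted, the report should say that either an effect of fracture on the reading or the larger number of events could explain it.

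**Cost.** One replaced sentence and two extra models on data already planned, plus the landmark analysis where possible. Without the landmark analysis, the TBS-change question becomes descriptive. The nonvertebral-only repeat loses 1.6/12.6 = 13% of events at a vertebral rate of 1.6%/year and 5/16 = 31% at 5%/year. For a true TBS-change rate ratio of 1.3 per SD (assumed, n=250), its simulated power is about 25%, against 27% and 32% with all fractures. A null result in either version would say little.

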## **Study Statistical Analysis**

**Official Title:** Zoledronic Acid for Osteoporotic Fracture Prevention (ZEST II)

**ClinicalTrials.gov ID (NCT number):** NCT02589600

**Document Date:** 3/30/2023

All statistical analyses will use SAS® version 9 (SAS Institute, Inc., Cary, North Carolina) based on intention-to-treat. First, appropriate descriptive statistics will be computed and graphical summarizations made for all variables for each treatment group for each time point as well as raw and percent change scores from baseline to obtain an overall sense of the distributional characteristics, missing values and general data quality. Second, baseline measures will be compared across arms using independent samples t- and a Wilcoxon rank sum tests, as appropriate, for continuous variables and chi-square and Fisher's exact tests, as appropriate, for categorical variables. Although no significant differences are expected due to randomization and large sample size, any variables found to be significantly different will be accounted for by including them as covariates in sensitivity analyses. Third, main analyses will be performed using a negative binomial regression model. Finally, exploratory analyses will be performed.
